#### Hepatic injury

A hepatic injury is defined by the following alterations of hepatic laboratory parameters:

- an elevation of AST (Aspartate Aminotransferase) and/or ALT (Alanine Aminotransferase) 23 fold ULN combined with an elevation of total bilirubin 22 fold ULN measured in the same blood draw sample, or
- aminotransferase (ALT, and/or AST) elevations 2:10 fold ULN.

#### **7.8.2      Laboratory data**

The analyses of laboratory data will be descriptive in nature and will be based on BI standards, 001-MCG-157: "Display and Analysis of Laboratory Data", current version, IDEA for CON. ill

#### **7.8.3      Vital signs**

Only descriptive statistics are planned for this section of the report.

#### **7.8.4      ECG**

ECGs will be evaluated locally by eCRF. Summary statistics will be displayed. Additional summaries will be produced for patients who have abnormal ECG findings at baseline or during the study period: patients with confirmed QT prolongation of QTc interval to greater than 450 ms in males or 470 ms in females.

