| Blood Gases/PaO ₂ data capture if performed as part of routine care | X | X | X | X | | | |
| 12-lead ECG ^{c,g} | X | X (±1 day) | Day 3,7,14,21 (±1 day) | X | | | |
| Physical Exam (refer to Section 5.2.1) | X | X (±1 day) | Day 3,7,14,21 (±1 day) | X | | | |
| Safety Laboratory Samples (refer to Section 5.2.3) ^{c,d} | X | X (±1 day) | Day 3,7,14,21 (±1 day) | X | | | |
| Pregnancy test (blood) for WOCBP ^{c,d} | X | | Day 7,14 (±1 day) | X | | | |
| Administration of trial medication ^e | | X | X | X ⁱ | | | |
| Termination of trial medication | | | | X | | | |
| Trial Completion | | | | | | | X |
| Vital Status | | | | | X | X | X |

EOT=End of Treatment; EOS=End of Study; FiO₂=fraction of inspired oxygen; FUP=Follow-up; PCR=polymerase chain reaction; PO₂=partial pressure of oxygen; SARS-CoV-2= severe acute respiratory syndrome coronavirus 2.

Footnotes:

^a EOT visit should be completed the day after the last dose of study drug is administered for all patients. EOT visit should occur no later than Day 29.

^b FUP 1 should be performed 4 days after EOT visit for all patients. FUP 2 and FUP 3 which correspond to study Day 15 and Day 29 after start of therapy, should be performed *if the time point is applicable after drug discontinuation*. FUP 2 and FUP 3 visits should not be conducted within +/- 2 days of EOT or FUP 1. FUP 4 and EOS which correspond to study Day 60 and Day 90 will be performed for all patients. If a patient remains hospitalized after EOT visit, applicable FUP visits and

Proprietary confidential information © 2021 Boehringer Ingelheim International GmbH or one or more of its affiliated companies

the EOS visit will be conducted in hospital until discharge and thereafter by telephone. Refer to [Section 6.2.3](#).

^c Laboratory tests and ECG performed up to 72 hours prior to enrolment will be accepted for determination of eligibility and the screening visit date may be the same day as Visit 2 or up to 3 days prior to Visit 2.

^d Results from laboratory tests performed as part of routine clinical care within the specified visit window may be used.

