3.3.3 Exclusion criteria

1. Alanine aminotransferase (ALT)/aspartate aminotransferase (AST) $> 5 \times$ the upper limit of normal (ULN).
2. Known active infection with HIV or hepatitis B or C.
3. Pulmonary oedema/respiratory failure due to cardiogenic insult.
4. Long-term oxygen therapy prior to current hospitalisation.
5. A confirmed baseline prolongation of QTc interval to greater than 450 ms in males or 470 ms in females, or any other relevant ECG finding at screening, or continued use of agents known to prolong the QT interval (refer to listing provided in ISF).
6. Stage 4 kidney disease or requiring dialysis (i.e., eGFR < 30 mL/min/1.73 m²).
7. History of the following cardiac conditions:
 - a) Myocardial infarction within 3 months prior to the first dose

¹ A woman is considered of childbearing potential (WOCBP), i.e. fertile, following menarche and until becoming post-menopausal unless permanently sterile.

Permanent sterilisation methods include hysterectomy, bilateral salpingectomy and bilateral oophorectomy.

Tubal ligation is NOT a method of permanent sterilisation.

A postmenopausal state is defined as no menses for 2 years without an alternative medical cause.

Proprietary confidential information © 2021 Boehringer Ingelheim International GmbH or one or more of its affiliated companies

- b) Unstable angina
- c) Clinically significant long QT features on electrocardiogram (ECG) or history of familial long QT
- 8. Anticipated transfer/discharge to another hospital or care facility other than their place of residence.
- 9. Not committed to full support or intubation (do not resuscitate/do not intubate wishes)
- 10. Allergy to study medication.
- 11. Relevant end-organ failure or other medical conditions (e.g. active cancer, cardiac, gastrointestinal) which based on investigator judgement would interfere with the conduct of this study.
- 12. Experimental, or off-label usage of medicinal products as specific treatments for COVID-19.
- 13. Currently enrolled in another investigational device or drug trial, or less than 30 days or 5 half-lives (whichever is shorter) since ending another investigational device or drug trial(s), or receiving other investigational treatment(s).
- 14. Women who are pregnant, nursing, or who plan to become pregnant while in the trial.

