3.3.4.1 Discontinuation of trial treatment

An individual patient will discontinue trial treatment if:

- The patient wants to discontinue trial treatment, without the need to justify the decision.
- The patient has repeatedly shown to be non-compliant with important trial procedures and, in the opinion of both, the investigator and sponsor representative, is not willing or able to adhere to the trial requirements in the future.
- The patient needs to take concomitant medication that interferes with the investigational medicinal product or other trial treatment.
- The patient can no longer receive trial treatment for medical reasons (such as surgery, adverse events, other diseases, or pregnancy).

Proprietary confidential information © 2021 Boehringer Ingelheim International GmbH or one or more of its affiliated companies

- The patient experiences renal impairment based on clinical judgement (e.g. sustained eGFR <30 mL/min/1.73 m²).
- The patient experiences hepatic impairment based on clinical judgement (e.g. ALT/AST >5 × ULN).
- The patient experiences QT prolongation of the QTc interval of either >60 ms change from baseline or greater than 500 ms during the study.

Should a patient become pregnant during the trial, study medication will be stopped and the patient will be followed up until birth or otherwise termination of the pregnancy. The data of the patient will be collected until Last Patient Completed and reported in the clinical trial report. Any events thereafter will be reported in the BI Pharmacovigilance database. For further details on pregnancy reporting, refer to [Section 5.2.6.2.3](#).

If new efficacy/safety information becomes available, Boehringer Ingelheim will review the benefit-risk-assessment and, if needed, pause or discontinue the trial treatment for all patients or take any other appropriate action to guarantee the safety of the trial patients.

Even if the trial treatment is discontinued, the patients remain in the trial and, given their agreement, will undergo the procedures for early treatment discontinuation, follow-up, and vital status collection as outlined in the [Flow Chart](#) and [Section 6.2.3](#).

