| Coagulation | D-dimer test Fibrinogen Activated partial thromboplastin time (aPTT) Prothrombin time (PT) International Normalised Ratio (INR) Protein C (activity as well as antigen, if available) Plasminogen activator inhibitor-1 (PAI-1) (activity) |
| Clinical Chemistry | Potassium Sodium Calcium Magnesium Phosphate Alkaline phosphatase Bicarbonate Creatinine Creatine kinase (MB fraction) eGFR (estimated by the CKD-EPI formula) Glucose Total bilirubin Aspartate aminotransferase (AST) Alanine aminotransferase (ALT) Gamma-glutamyl transferase (GGT) C-reactive protein (regular test) Ferritin Triglycerides Lactate dehydrogenase (LDH) Troponin (I) |

5.2.4 **Electrocardiogram**

The 12-lead ECGs must be administered by a qualified technologist and results will be recorded as scheduled in the [Flow Chart](#). ECGs should be performed 0.5-4 hours after drug administration. The investigator or a designee will evaluate whether the ECG is normal or abnormal and assess clinical relevance. ECGs may be repeated for quality reasons and a repeated recording used for safety evaluation.

Additional ECGs may be recorded for safety reasons. Dated and signed printouts of ECG with findings should be documented in patient's medical record. The aggregate PR, QRS, QT, RR, QTcF, and QTcB interval data, as available, from the local ECG readout will be recorded in the eCRF for safety evaluation.

Clinically relevant abnormal findings will be reported either as baseline condition (if identified at the screening visit) or otherwise as AEs and will be followed up and/or treated as medically appropriate.

Refer to [Section 3.3.4.1](#) for treatment discontinuation criteria regarding QT prolongation.

5.2.5 **Other safety parameters**

Not applicable

5.2.6 **Assessment of adverse events**

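### SAP 7.8.4 categorises QTc only by the trial's entry cut-off (450/470 ms), so patients who reach the protocol's discontinuation thresholds (>500 ms or a rise >60 ms) are not reported separately

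*SAP*

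**What the plan says.** SAP 7.8.4 plans two kinds of ECG output. The first is general: "Summary statistics will be displayed". The second is an additional summary of patients with abnormal findings at baseline or during the study, specified as "patients with confirmed QT prolongation of QTc interval to greater than 450 ms in males or 470 ms in females".

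These figures, and the word *confirmed*, match exclusion criterion 5 in protocol 3.3.3: "A confirmed baseline prolongation of QTc interval to greater than 450 ms in males or 470 ms in females".

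Protocol 3.3.4.1 uses different limits for stopping trial treatment: "QT prolongation of the QTc interval of either >60 ms change from baseline or greater than 500 ms during the study". Protocol 5.2.4, the ECG section, refers the reader to those limits.

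On the data, protocol 5.2.4 says: "The aggregate PR, QRS, QT, RR, QTcF, and QTcB interval data, as available, from the local ECG readout will be recorded in the eCRF". SAP 7.8.4 does not say which of the two corrections its cut-off applies to. SAP 6.7 defines baseline for efficacy endpoints and for safety laboratory values, but not for ECG.

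**The concern.** Safety is part of the main objective (protocol 2.1.1), and the protocol builds QT into its exclusion criteria, its ECG schedule and its discontinuation rules. A reader of the trial report will want to know how many patients in each arm reached the trial's own QT rule. The planned table answers a different question: how many crossed the line below which patients were admitted. A patient at 455 ms and one at 510 ms fall in the same row, and a patient with a large rise from a low baseline may be in no row.

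The row is also not fully reproducible as written. The correction formula is not named, *confirmed* is not defined, and no ECG baseline is given from which a change could be computed.

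**Working it through.** The plan states no QTc rate, so there is no figure to reproduce. The check compares the definitions first and then asks whether the size can be established.

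**1. Values above 500 ms.** Any QTc above 500 ms is also above 450 and 470 ms. If confirmed, it is inside the SAP count but not distinguishable from a value just over the cut-off. The rule in protocol 3.3.4.1 does not carry the word *confirmed*, so a single reading above 500 ms could meet the protocol rule without entering the SAP row.

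**2. Rises above 60 ms.** Let b be baseline and p the on-treatment peak. The protocol rule is met when p > b + 60. The patient stays outside the SAP count when p ≤ 450 (men) or p ≤ 470 (women). Both hold together only if:
- men: b + 60 < 450, so b < 390 ms;
- women: b + 60 < 470, so b < 410 ms.

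Example: a man going from 380 to 445 ms rises by 65 ms, meets the protocol rule and is not counted. From a baseline of 390/410 ms or higher, a rise of more than 60 ms always crosses the cut-off.

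**3. Correction formula.** QTcF = QT/RR^(1/3) and QTcB = QT/RR^(1/2), so QTcB/QTcF = RR^(−1/6). At 100 beats/min RR = 60/100 = 0.6 s and the ratio is 0.6^(−1/6) = 1.089. A QTcF of 450 ms is then a QTcB of 450 × 1.089 = 490 ms. The same tracing can be outside the row by one formula and well inside it by the other.

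**4. Baseline.** Protocol 7.2.1 gives a general definition: the last measurement before randomisation. ECGs are to be recorded 0.5 to 4 hours after dosing (protocol 5.2.4), so a Visit 2 ECG taken to that rule is already on treatment. A change from baseline therefore needs an explicit pre-dose reference.

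**5. Size.** The documents give no QTc mean or variability. A simulation (400,000 patients per scenario) used these assumptions: normal QTc; means of 405/420 or 420/435 ms (men/women); between-patient SD 18 ms; within-patient SD 8, 12 or 18 ms; 60% men; 2 or 6 on-treatment ECGs; entry ECG at or below the cut-off; mean drug shift of 0 or 20 ms.

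| Share of patients | No shift | 20 ms shift |
|---|---|---|
| Any single ECG >450/470 ms | 0.9% to 28% | 11% to 66% |
| Same, exceeded again on an immediate repeat | 0.2% to 8.2% | 6% to 37% |
| >500 ms or rise >60 ms | 0.0% to 5.2% | 0.1% to 26% |

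Under the 20 ms shift, and counting any single crossing, 0.4% to 33% of patients in the 450/470 ms row also meet the protocol rule. Of the patients who meet the rule, 47% to 95% lie inside the row. The ranges are too wide to give a figure for this trial. They do show that the count at one threshold does not determine the count at the other.

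**6. What the added rows could show.** With 65 patients per arm, the chance of seeing at least one case is 1 − (1 − p)^65. This is 48%, 73%, 86% and 96% for true rates p of 1%, 2%, 3% and 5%.

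**The case against.** Two stronger readings are tempting, and neither is supported.

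- A reader might infer that patients who met the discontinuation rule are never counted. Steps 1 and 2 show otherwise: confirmed values above 500 ms are in the count, and so are confirmed crossings by patients whose rise above 60 ms started from 390/410 ms or higher. What is missing is a separate count.
- A reader might infer that the 450/470 ms row would mostly hold random drift. That depends on variability figures that the documents do not give, and on what *confirmed* means. If it means a repeat ECG, the no-effect crossing rate in step 5 falls from 0.9%–28% to 0.2%–8.2%.

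It is also fair to say that this can only be called the sole QTc category in the visible text. Parts of the SAP are not public, protocol 7.2.5 contains a redaction, and that section refers to sponsor standards that cannot be seen here.

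Other outputs help in part. The reason for stopping treatment must be recorded in the CRF (protocol 3.3.4). The SAP tabulates adverse events that led to discontinuation (7.8.1). The summary statistics include a maximum (SAP 7). The DMC reviews safety data (protocol 8.7). None of these guarantees the number. A maximum shows that someone exceeded 500 ms, not how many did. An ECG change becomes an adverse event only when the investigator considers it clinically relevant (protocol 5.2.4 and 5.2.6.1.1), and protocol 3.3.4.1 lists QT prolongation apart from adverse events as a reason to stop. A change that stops treatment would plausibly be reported as an event, but the text does not ensure it.

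Finally, safety analyses are descriptive and the intervals are already collected, so the counts could be produced at reporting without loss. That stands, and it limits the weight of the point.

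**Conclusion.** The point holds as a gap in reporting. In the visible text, SAP 7.8.4 and protocol 3.3.4.1 use different QTc limits, and the per-arm number of patients reaching the protocol's limits cannot be recovered from the planned outputs. Values above 500 ms are pooled with milder ones. Rises above 60 ms from a baseline below 390 ms (men) or 410 ms (women) can be missed. These statements follow from the definitions and need no assumption about QTc variability.

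The number of patients affected cannot be established, because it rests on distributions that the documents do not give. The primary analysis is unaffected. No view is taken on which QTc threshold is clinically right; the point is that the two sections should be reconciled. It is worth doing because it is cheap and safety is a stated objective.

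**What to change.** Reconcile SAP 7.8.4 with protocol 3.3.4.1 by tabulating, for each arm, the number and percentage of patients with:
- a maximum on-treatment QTc above 500 ms;
- an increase of more than 60 ms from the last pre-dose ECG;
- either of these.

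Keep the 450/470 ms row. State one correction, QTcF or QTcB, for all QTc rows; give the ECG baseline explicitly; and say what makes a prolongation *confirmed* and which rows need confirmation.

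The cost is a few rows in one descriptive table and two or three sentences in the SAP. The intervals are already planned for the eCRF, so no new data are needed. The only drawback is a slightly longer ECG output.

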#### **7.8.5      Others**

Frequency of patients with extrapulmonary organ failure (based on reported AEs) will be summarized descriptively by treatment group and organ class: cardiovascular failure, CNS failure, renal failure, hepatic failure, and coagulation abnormalities.

## **8. TIMEPOINT OF RELEASE OF TREATMENT INFORMATION**

Once the last patient has completed their End-of-Treatment (EOT) visit and all corresponding data has been entered and cleaned to the level documented in the "Data Delivery Request" (DDR) form, the data will be declared ready to be unblinded via the "Data Ready to be Unblinded and/or Final Trial Closure Notification" (RUN) form. Snapshot will be at EOT or any time after once thresholds are met (including Day 29 data thresholds). Then the treatment information will be released for analysis.

The data collection for the off-treatment residual effect period until the End-of-Study (EoS)/ Follow-Up visit will continue into the unblinded trial database. Once trial data collection has been completed and all data has been entered and cleaned as documented on the RUN form, a final data lock will be performed.

After the release of treatment information, it is expected that only trial data related to the off-treatment residual effect period will be entered and changed. Therefore, after the timepoint of release of treatment information, all changes affecting trial data up to the End-of-Treatment (EoT) visit will be documented and summarized in the CTR.

**11. HISTORY TABLE****Table 11: 1 History table**

Version	Date (DD-MMM-YY)	Author	Sections changed	Brief description of change
Initial	08-APR-2021	[REDACTED]	None	This is the final TSAP

**Boehringer  
1111/ Ingelheim**

